I agree to ensure that the confidential information contained in this document will not be used for any purpose other than the evaluation or conduct of the clinical investigation without the prior written consent of Amgen Inc.

Signature

Name of Investigator

Date (DD Month YYYY)

Protocol Synopsis

Title: A Randomized, Open-label, Phase 3 Study Comparing Carfilzomib, Dexamethasone, and Daratumumab to Carfilzomib and Dexamethasone for the Treatment of Patients With Relapsed or Refractory Multiple Myeloma (CANDOR)

Study Phase: 3

Indication: Relapsed or Refractory Multiple Myeloma

Primary Objective: The primary objective is to compare carfilzomib, dexamethasone, and daratumumab (KdD) to carfilzomib and dexamethasone (Kd) in terms of progression free survival (PFS) in patients with multiple myeloma who have relapsed after 1 to 3 prior therapies.

Secondary Objective(s): Key secondary objectives are to compare the following between the 2 arms:

- Overall Response Rate (ORR; defined as the proportion of best overall response of stringent complete response [sCR], complete response [CR], very good partial response [VGPR], and partial response [PR])
- rate of minimal residual disease negative-complete response (MRD[-]CR) in bone marrow aspirates at 12 months (\pm 4 weeks) as determined by Next-Generation sequencing (NGS)
- overall survival (OS)

Additional secondary objectives are to compare the following between the 2 arms:

- safety and tolerability
- duration of response (DOR)
- time to next treatment
- time to progression (TTP)
- time to response
- persistence of MRD[-]CR
- complete response rate (CRR)
- MRD[-] rate
- quality of life

Hypothesis: The KdD regimen will provide significant improvement in PFS over the Kd regimen.

Primary Endpoint: PFS defined as time from randomization until disease progression or death from any cause. Response and disease progression determined by a blinded Independent Review Committee (IRC).

Secondary Endpoint(s): Key secondary endpoints include:

- ORR: defined as the proportion of best overall response of stringent complete response (sCR), complete response (CR), very good partial response (VGPR), and partial response (PR) by IRC
- MRD[-]CR rate, MRD[-]CR defined as achievement of CR by IRC per International Myeloma Working Group-Uniform Response Criteria (IMWG-URC) and MRD[-] status as assessed by NGS (at a 10^{-5} level, pending analytical validation) at 12 months
- OS

Additional secondary endpoints:

- DOR
- time to next treatment
- TTP
- time to response
- sustained MRD[-]CR (defined as the proportion of subjects that maintain MRD[-]CR for 12 months or more after achieving MRD[-]CR status)
- CRR (defined as the proportion of best overall response of sCR or CR)
- MRD[-] rate
- electronic clinical outcome assessments (eCOAs): quality of life questionnaire – core 30 items (QLQ-C30) Global Health Status/Quality of Life (QoL) measured by European Organisation for Research and Treatment of Cancer (EORTC) QLQ-C30 version 3 questionnaire
- subject incidence of treatment-emergent adverse events
- safety laboratory values, left ventricular ejection fraction (LVEF), forced expiratory volume in 1 second (FEV1)/forced vital capacity (FVC) ratio, and vital signs at each scheduled assessment

Study Design: This is a phase 3 multicenter, open-label, randomized study in subjects with relapsed or refractory multiple myeloma (RRMM) who have received 1 to 3 prior therapies.

Subjects will be randomized in a 2:1 ratio to 1 of 2 arms:

- Arm 1: KdD
- Arm 2: Kd

Randomization will be performed using an interactive voice/web response system (IxRS) and subjects will be stratified based on the following criteria: Original International Staging System (ISS) stage (variables: albumin and beta 2 microglobulin; strata: Stage 1 or 2 vs Stage 3) at screening, prior proteasome inhibitor exposure (yes vs no), number of prior lines of therapy (1 vs ≥ 2), and prior cluster differentiation antigen 38 (CD38) antibody therapy (yes vs no).

Subjects will receive the **study** treatment determined by randomization [REDACTED] or until confirmed disease progression, unacceptable toxicity, withdrawal of consent, or death (whichever occurs first). No crossover between the treatment arms will be allowed. All subjects will be assessed for multiple myeloma disease response according to the IMWG-URC using central laboratory test results every 28 ± 7 days. [REDACTED] disease response assessments will be performed every 28 ± 7 days until confirmed progressive disease (PD).

Following progression or discontinuation of study drug(s), subjects will have 1 follow-up visit (30 days [+ 3] after last dose of all study drug[s]). **After disease progression**, data on survival status and subsequent antimyeloma therapy will be gathered at [REDACTED].

Local serology testing for hepatitis B surface antigen, hepatitis B surface antibody, and hepatitis B core antibody **will be performed** at the next scheduled visit for all subjects that do not already have a **known** medical history of hepatitis B infection or who have not had testing conducted within the previous 12 weeks. In addition, subjects with a **known medical** history of hepatitis B infection or who test positive for hepatitis B virus (HBV) serologies will be monitored closely for signs and symptoms of hepatitis B and will have local HBV **deoxyribonucleic acid (DNA)** testing performed at their next visit and then every 12 **weeks (± 2 weeks) or more frequently if clinically indicated through follow-up Visit 1. Subjects in arm 1 (KdD) will continue to be**

monitored and tested for 6 months following the last dose of daratumumab. A hepatitis specialist should be consulted for all subjects who test positive for HBV serology or HBV DNA to undergo full assessment and make decisions regarding HBV reactivation treatment and/or confirmation whether HBV reactivation is adequately controlled to resume study drugs. Subjects who have received Hepatitis B vaccination with only anti-HBs positivity and no clinical signs of hepatitis do not require HBV DNA monitoring.

Sample Size: Approximately 450 subjects will be enrolled (300 in arm 1 and 150 in arm 2).

Summary of Subject Eligibility Criteria:

Key Inclusion Criteria

- male or female subjects \geq 18 years of age
- relapsed or progressive multiple myeloma after last treatment
- received at least 1 but not more than 3 prior lines of therapy for multiple myeloma (induction therapy followed by stem cell transplant and consolidation/maintenance therapy will be considered as 1 line of therapy; see [Appendix E](#) for guidance)
- prior therapy with carfilzomib is allowed as long as the patient had at least a PR to most recent therapy with carfilzomib, was not removed due to toxicity, did not relapse within 60 days from discontinuation of carfilzomib, and will have at least a 6-month carfilzomib treatment-free interval from last dose received until first study treatment. (Patients may receive maintenance therapy with drugs that are not proteasome inhibitors or CD38 antibodies during this 6-month carfilzomib treatment free interval)
- prior therapy with anti-CD38 antibodies is allowed as long as the patient had at least a PR to most recent therapy with CD38 antibody, was not removed due to toxicity, did not relapse within 60 days from intensive treatment (at least every other week) of CD38 antibody therapy, and will have at least a 6-month CD38 antibody treatment-free interval from last dose received until first study treatment.

Key Exclusion Criteria

- prior participation in a Janssen daratumumab phase 3 study (with exception of subjects in control arm that have withdrawn consent from study participation)
- known moderate or severe persistent asthma within the past 2 years
- known chronic obstructive pulmonary disease (COPD) with a FEV1 < 50% of predicted normal
- active congestive heart failure (New York Heart Association [NYHA] Class III to IV), symptomatic ischemia, uncontrolled arrhythmias, clinically significant electrocardiogram (ECG) abnormalities, screening ECG with corrected QT interval (QTc) of > 470 msec, pericardial disease, or myocardial infarction within 4 months prior to randomization

For a full list of eligibility criteria, please refer to [Section 4](#).

Investigational Product

Amgen Investigational Product Dosage and Administration:

Carfilzomib will be administered as an intravenous (IV) infusion. On days when more than 1 investigational product is administered, the required order of administration is as follows: dexamethasone, pre-infusion medications for daratumumab, carfilzomib, daratumumab, and post-infusion medications for daratumumab.

Carfilzomib will be dosed twice weekly over 30 ± 5 minutes, on days 1, 2, 8, 9, 15, and 16 of each 28-day cycle. The administration may be within ± 2 days for each scheduled dose. The dose will be 20 mg/m² on cycle 1 days 1 and 2 and 56 mg/m² beginning on cycle 1 day 8 and thereafter.

Each subject's first dose of carfilzomib will be calculated based upon baseline body surface area (BSA) using the Mosteller formula. In subjects with BSA of greater than 2.2 m², the dose should

be capped based on a BSA of 2.2 m². The dose for each subject should not be revised unless the subject experiences a change in body weight of > 20% in which case the BSA and dose should be recalculated. The dose can also be modified in response to toxicity following the dose modification guideline tables.

Non-Amgen Investigational Product Dosage and Administration:

Daratumumab will be administered as an IV infusion. On days 1 and 2 of cycle 1, daratumumab will be administered at 8 mg/kg in 500 mL normal saline each day. The dose of 16 mg/kg in 500 mL normal saline will be given once weekly as a single infusion for the remaining doses of the first 2 cycles (ie, days 8, 15, and 22 of cycle 1; and days 1, 8, 15, and 22 of cycle 2), then every 2 weeks for 4 cycles (cycles 3 to 6), and then every 4 weeks for the remaining cycles or until disease progression. The administration may be within \pm 2 days for each scheduled dose.

Non-investigational Product

Non-Amgen Non-investigational Product Dosage and Administration:

Dexamethasone 40 mg will be taken orally (PO) or by IV infusion weekly. The IV administration of dexamethasone must be given on cycle 1 days 1 and 2. Dexamethasone IV or PO will be given on successive days at 20 mg each treatment day on weeks with carfilzomib and/or daratumumab infusions. All subjects regardless of age will be required to receive 20 mg of dexamethasone on days 1 and 2 of cycle 1 (as a preinfusion medication for daratumumab infusion) followed by 20 mg of methylprednisolone or equivalent on the third day. For Subjects > 75 years of age or subjects whose weekly dexamethasone dose has been reduced to 20 mg/week, 20 mg of dexamethasone will be given as a preinfusion medication for daratumumab infusion, followed by 8 mg of dexamethasone prior to carfilzomib infusion on days 9 and 16 of cycle 1.

Starting with cycle 2, 20 mg dexamethasone must be given on days daratumumab is administered (without 8 mg dose on subsequent carfilzomib dosing day), otherwise the 20 mg dose can be split across carfilzomib dosing days.

For days when dexamethasone is given in the absence of other IV infusion (neither carfilzomib nor daratumumab is scheduled), it may be given within \pm 2 days for each scheduled dose. Dexamethasone will be administered at least 30 minutes (but no more than 4 hours) prior to carfilzomib and within 1 to 3 hours from the daratumumab dose.

When carfilzomib is permanently discontinued, dexamethasone may be omitted on days when given in the absence of daratumumab based on their assessment of the subject's steroid tolerance.

For subjects in arm 1 on cycles 7+ without previous infusion-related reaction (IRR), dexamethasone premedication may be decreased or omitted, if the subject cannot tolerate 20 mg of dexamethasone or equivalent.

Procedures: Written informed consent must be obtained from all subjects or legally acceptable representatives before any study specific screening procedures are performed. The following procedures will occur per the Schedule of Assessments: medical history, complete physical examination, physical measurements, vital signs, Eastern Cooperative Oncology Group performance status (ECOG PS), ECG, echocardiogram (ECHO), pulmonary function tests (PFTs), recording of concomitant medications, review of adverse events and serious adverse events. Electronic clinical outcome assessments **will no longer be collected after protocol Amendment 6**. Imaging studies for bone lesions (all subjects) and soft tissue plasmacytoma evaluation (if clinically indicated). Central laboratory testing will be performed to confirm disease and stage including bone marrow with samples for MRD and fluorescence in-situ hybridization (FISH). Additional central laboratory testing will include hematology, serum chemistry, hepatic and renal function. Local laboratory testing will include coagulation factors, pregnancy testing, blood typing with indirect antiglobulin test (IAT), HBV serologies, and HBV DNA testing. Samples will also be taken to perform pharmacokinetic (PK), pharmacodynamic (PDn), biomarker studies, and anti-daratumumab antibody assessments. Subjects will be assessed for survival status and subsequent antineoplastic therapies will be collected during LTFU.

For a full list of study procedures, including the timing of each procedure, please refer to [Section 7](#) and the Schedule of Assessments ([Table 11](#)).

Statistical Considerations:

The efficacy analyses of PFS and key secondary endpoints will be conducted on the full analysis set. Treatment effects in efficacy endpoints will be evaluated and compared KdD vs Kd. For PFS, response and disease progression will be determined by an IRC in a blinded manner. In addition, response and disease progression outcomes will be determined locally by investigators in an unblinded manner and centrally by the sponsor using a validated computer algorithm (Onyx Response Computer Algorithm [ORCA]) in a blinded manner. The primary analysis of PFS will be based on IRC assessed outcomes; the timing will be event driven and will happen when approximately 188 PFS events are reached. The PFS outcomes assessed by the investigators as well as by ORCA will serve as supportive analyses of PFS.

The primary comparison of PFS will be tested using a log rank test stratified by the randomization stratification factors per IxRS at 1-sided significance level of 0.025.

If PFS is significant, the key secondary endpoints will be tested by hierarchical testing in the order of ORR, MRD[-]CR by NGS, and OS. Overall response rate and MRD[-]CR will be tested once at the time when primary analysis of PFS is significant. If PFS, ORR, and MRD[-]CR are all statistically significant at 0.025 significance level, then OS will be tested multiple times with an overall alpha of 0.025.

[REDACTED]

[figure not shown]
Overall response rate and MRD[-]CR will be analyzed using the Cochran-Mantel-Haenszel chi-square test controlling for the randomization stratification factors per IxRS. Overall survival will be analyzed using the same method as described for the PFS endpoints.

Safety data, including laboratory test results, vital signs, treatment-emergent adverse events, serious adverse event and treatment related events, will be summarized by actual treatment received. Analysis on changes on LVEF and PFTs over time will be conducted.

For a full description of statistical analysis methods, please refer to [Section 10](#).

Sponsor: Amgen, Inc.
Data Element Standards Version 5.0, 20 March 2015
Version(s)/Date(s):

Study Schema

Ab = antibody; CD38 = cluster differentiation antigen 38; CR = complete response; d = dexamethasone; D = daratumumab; **DCO = data cutoff**; ISS = International Staging System; K = carfilzomib; MRD = minimal residual disease; MRD[-]CR = minimal residual disease negative-complete response; ORR = overall response rate; OS = overall survival; PFS = progression-free survival; PI = proteasome inhibitor; RRMM = relapsed or refractory multiple myeloma.

^a For patients with baseline chronic hepatic impairment (mild, moderate), reduce the starting and subsequent doses of carfilzomib by 25% (ie, 15 mg/m² day 1 and 2 of cycle 1 and 42 mg/m² day 8 cycle 1 and thereafter).

Study Glossary

Abbreviation or Term	Definition/Explanation
ADCC	antibody-dependent cellular cytotoxicity
ADCP	antibody-dependent cellular phagocytosis
ALT	alanine aminotransferase
ANC	absolute neutrophil count
anti-HBc	hepatitis B core antibody
anti-HBs	hepatitis B surface antibody
AST	aspartate aminotransferase
BSA	body surface area
CD38	cluster differentiation antigen 38
CDC	complement dependent cytotoxicity
CI	confidence interval
COPD	chronic obstructive pulmonary disease
CR	complete response
CrCl	creatinine clearance
CRF	case report form
CRR	complete response rate
CT	computed tomography
CTCAE	Common Terminology Criteria for Adverse Events
ctDNA	circulating tumor DNA
DCO	data cutoff
DLCO	diffusing capacity of the lungs for carbon monoxide
DMC	Data Monitoring Committee
DNA	deoxyribonucleic acid
DOR	duration of response
DTT	dithiothreitol
ECG	electrocardiogram
ECHO	echocardiogram
eCOA	electronic clinical outcome assessment
ECOG	Eastern Cooperative Oncology Group
eCRF	electronic case report form
EDC	electronic data capture
ELISA	enzyme-linked immunosorbent assay
End of Study	defined as the date when the last subject is assessed or receives an intervention for evaluation in the study (ie, last subject last visit)

Abbreviation or Term	Definition/Explanation
End of Study for Individual Subject	defined as the last day that protocol-specified procedures are conducted for an individual subject
EORTC	European Organisation for Research and Treatment of Cancer
ESC	European Society of Cardiology
ESH	European Society of Hypertension
FC	flow cytometry
FCBP	females of childbearing potential
FcR	Fc receptor
FDG-PET	fluorodeoxyglucose-positron emission tomography
FEV1	forced expiratory volume in 1 second
FISH	fluorescence in-situ hybridization
FSH	follicle stimulating hormone
FVC	forced vital capacity
GCP	Good Clinical Practice
gDNA	genomic DNA
HBsAg	hepatitis B surface antigen
HBV	hepatitis B virus
Heart rate	number of cardiac cycles per unit of time
HIV	human immunodeficiency virus
HR	hazard ratio
HRT	hormonal replacement therapy
IB	Investigator's Brochure
ICF	informed consent form
ICH	International Council for Harmonisation
ICMJE	International Committee of Medical Journal Editors
IFE	immunofixation
Ig	immunoglobulin
IMiD	immunomodulatory drug
IMWG-URC	International Myeloma Working Group-Uniform Response Criteria
INR	international normalized ratio
Interactive Voice Response (IVR)	telecommunication technology that is linked to a central computer in real time as an interface to collect and process information.
Interactive Web Response (IWR)	web based technology that is linked to a central computer in real time as an interface to collect and process information.
IRB/IEC	institutional review board/independent ethics committee

Abbreviation or Term	Definition/Explanation
IRC	Independent Review Committee
IRR	infusion-related reaction
ISS	International Staging System
IUD	intrauterine device
IUS	intrauterine hormonal-releasing system
IV	intravenous
IxRS	interactive voice/web response system
Kd	20/56 mg/m² twice weekly carfilzomib and dexamethasone
KdD	20/56 mg/m ² twice weekly carfilzomib, dexamethasone, and daratumumab
K-M	Kaplan-Meier
KRd	carfilzomib, lenalidomide, and dexamethasone
LDH	lactate dehydrogenase
LD WBCT	low-dose whole body computed tomography
LTFU	long-term follow-up
LVEF	left ventricular ejection fraction
MDSC	myeloid-derived suppressor cells
MoA	mechanisms of action
MR	minimal response
MRD	minimal residual disease
MRD[-]CR	minimal residual disease negative-complete response; defined as achievement of CR (includes sCR) per International Myeloma Working Group-Uniform Response Criteria (IMWG-URC) and MRD[-] status as assessed by NGS (at a 10 ⁻⁵ level, pending analytical validation)
MRI	magnetic resonance imaging
MTD	maximum tolerated dose
NE	not evaluable
NGS	Next-Generation sequencing
NK	natural killer
NT-proBNP	N-terminal of the prohormone brain natriuretic peptide
NYHA	New York Heart Association
ORCA	Onyx Response Computer Algorithm
ORR	overall response rate
OS	overall survival
PBMCs	peripheral blood mononuclear cells
PD	progressive disease
PDn	pharmacodynamics

Abbreviation or Term	Definition/Explanation
PET	positron emission tomography
PFS	progression free survival
PFT	pulmonary function test
PJP	pneumocystis jiroveci pneumonia
PK	pharmacokinetic
PO	orally
POEMS	polyneuropathy, organomegaly, endocrinopathy, monoclonal protein, and skin changes
POR	proof of receipts
PR	partial response
Primary Completion	defined as the date when the last subject is assessed or receives an intervention for the final collection of data for the primary endpoint(s), for the purposes of conducting the primary analysis, whether the study concluded as planned in the protocol or was terminated early
PR interval	PR interval is measured from the beginning of the P wave to the beginning of the QRS complex in the heart's electrical cycle as measured by ECG
PS	performance status
PSA	prostate specific antigen
QLQ-C30	quality of life questionnaire – core 30 items
QoL	quality of life
QRS interval	QRS interval the interval between the Q wave and the S wave in the heart's electrical cycle as measured by ECG; represents the time it takes for the depolarization of the ventricles
QTc interval	QT interval corrected for heart rate using accepted methodology

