6.2.2 Non-Amgen Investigational Product: Daratumumab

6.2.2.1 Daratumumab: Dosage, Administration, and Schedule

Daratumumab will be administered as an IV infusion. On days when more than 1 investigational products are administered, the required administration is as follows: dexamethasone, other pre-infusion medications for daratumumab, carfilzomib, daratumumab, and post-infusion medications for daratumumab.

- On days 1 and 2 of cycle 1, daratumumab will be administered at 8 mg/kg in 500 mL normal saline each day.
 - If the subject's first 2 infusions of 8 mg/kg daratumumab are well-tolerated (defined as an absence of infusion-related reaction [IRR] > grade 1), the first infusion of 16 mg/kg in 500 mL normal saline will be given once weekly as a

single infusion for the remaining doses of the first 2 cycles, ie, days 8, 15, and 22 of cycle 1; and days 1, 8, 15, and 22 of cycle 2, then every 2 weeks for 4 cycles (cycles 3 to 6), and then every 4 weeks for the remaining cycles or until disease progression.

- If the 8 mg/kg infusions are not well-tolerated (defined as IRR > grade 1), the dilution will be in 1000 mL of normal saline until the subject completes an infusion without > grade 1 IRR. For any infusions that would require a large volume (eg, 1000 mL); the daratumumab dose may be divided in 2 days.

The administration may be within \pm 2 days for each scheduled dose. See [Table 13](#) to review the arm 1 dosing schedule.

Each subject's dose will be calculated based on the subject's weight rounded to the nearest kilogram. Dosing calculations do not need to be changed for weight changes that are < 10% from baseline. The pharmacist will calculate the required volume and number of vials needed. The daratumumab infusion rates are provided in [Table 5](#) and [Table 6](#).

The planned dose (mg/kg), dose (mg), start date/time, stop date/time, reason for change in planned dose, reason for dose change/withheld, reason for dose delay, reason for dose interruption and package lot number of daratumumab is to be recorded on each subject's eCRF.

Table 5. Daratumumab Infusion Rate

C1D1 and C1D2 (8 mg/kg)		C1D8 (16 mg/kg)		Subsequent Infusions	
Time (minutes)	mL/hr	Time (minutes)	mL/hr	Time (minutes)	mL/hr
0 – 60	50	0 – 60	50 ^a	0 - 60	100 ^b
61 – 120	100	61 – 120	100	61 - 120	150
121 – 180	150	121 - 180	150	121 - 180	200
181 – 240	200	181 - 240	200	181-	200
500 mL		500 mL ^a		500 mL	

CxDx = cycle X day X; IRR = infusion-related reaction.

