^a If the subject's first 2 infusions of 8 mg/kg daratumumab are well-tolerated (defined as an absence of IRR > grade 1), the first infusion of 16 mg/kg daratumumab will be administered at an initial rate of 50 mL/hour and increased by 50-mL/hour increments at 60-minute intervals, as tolerated, to a maximum rate of 200 mL/hour. If the 8 mg/kg infusions are not well-tolerated (defined as IRR > grade 1), the dose may be split in 2 days (on 500 mL each day).

^b Modified rates should only be used if at least 1 16 mg/kg infusions of daratumumab was well-tolerated as defined by an absence of >grade 1 infusion-related reactions during a final infusion rate of \geq 100 mL/hr.

The duration of infusion may be shortened starting in cycle 2 onwards to a 90-minute infusion for subjects without a history of an infusion related reaction after the third dose of daratumumab.

The 90-minute daratumumab accelerated infusions (Barr et al, 2017) can be administered at an initial rate of 20% of the total dose over 30 minutes, followed by the remaining 80% of the total dose over 60 minutes (90-minute total infusion time).

- Rapid infusion will be given in a total volume of 500 mL
- This allows for a rate of 200 mL/hour for the first 30 minutes and a rate of 400 mL/hour for the final 60 minutes.
- If a subject experiences any grade infusion related reaction, the subject will not be eligible to receive additional rapid infusions until he/she has received standard infusion daratumumab without any grade hypersensitivity reaction.

Table 6. Accelerated/Shortened Infusion Rate

Accelerated/Shortened Infusion	Dilution Volume	Initial Infusion Rate (first 30 minutes)	Subsequent Infusion Rate (last 60 minutes)	Maximum Infusion Rate
	500 mL	200 mL/hour	400 mL/hour	400 mL/hour

Rapid infusion will be given in a total volume of 500 mL. This allows for a rate of 200 mL/hour or the first 30 minutes and a rate of 400 mL/hour for the final 60 minutes. If a subject experiences any grade infusion related reaction, he/she is not eligible to receive additional rapid infusions until they have received standard infusion daratumumab without any grade hypersensitivity reaction.

Source: Barr et al, 2017.

See Section 7.3.10 for details on vital sign monitoring during daratumumab and other infusions.

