Cycle 1	X	X	X	X	X	X		Not required for days when daratumumab is administered
Dexamethasone IV or PO (40 mg/week)								
All cycles	20	20	20	20	20	20	40	Dexamethasone 40 mg will be taken weekly (20 mg each day when taken on successive days). Cycle 1: All subjects, regardless of age, will receive 20 mg C1D1 and C1D2, followed by 20 mg methylprednisolone on C1D3.
Dexamethasone IV or PO (20 mg/week) – for subjects > 75 years of age								
Cycle 1	20	20	20	8	20	8	20	Cycle 1: All subjects will receive 20 mg C1D1 and C1D2, followed by 20 mg methylprednisolone on C1D3. 20 mg will be given as a preinfusion medication for daratumumab infusion, followed by 8 mg of dexamethasone prior to carfilzomib infusion on C1D9 and C1D16. Cycle 2+: 20 mg must be given as a preinfusion medication for daratumumab infusion (without 8 mg dose on subsequent carfilzomib dosing day), otherwise the 20 mg dose can be split across carfilzomib dosing days (eg, 12/8, 10/10, etc).
Cycle 2	20	-	20	-	20	-	20	
Cycles 3 to 6	20	-	12	8	20	-	20	
Cycles 7+	20	-	12	8	12	8	20	
Carfilzomib IV								
Cycle 1	20	20	56	56	56	56		The dose ^a will be 20 mg/m ² on C1D1 and C1D2 and 56 mg/m ² beginning on C1D8 and thereafter.
Cycle 2+	56	56	56	56	56	56		
Daratumumab IV								
Cycle 1	8	8	16		16		16	For pre/post-infusion medication guidance, see Sections 6.2.2.1.1 and 6.2.2.1.2. C1D1 and C1D2: 8 mg/kg in 500 mL NS will be administered each day. Thereafter, daratumumab will be given 16 mg/kg per dose diluted in 500 mL NS. Daratumumab infusions begin after carfilzomib infusions are completed.
Cycle 2	16		16		16		16	
Cycles 3 to 6	16				16			
Cycles 7+	16							

CxDx = cycle X day X; IV = intravenous; KdD = carfilzomib, dexamethasone, and daratumumab; NS = normal saline; PO = by mouth.

^a For patients with baseline chronic hepatic impairment (mild, moderate), reduce the starting and subsequent doses of carfilzomib by 25% (ie, 15 mg/m² day 1 and 2 of cycle 1 and 42 mg/m² day 8 cycle 1 and thereafter).

Table 14. Dosing Schedule - Arm 2 (Kd)

Investigational Products and Other Protocol-required Therapies	Dosing Cycle Day							Notes
	1	2	8	9	15	16	22	
IV predose and postdose hydration (for carfilzomib as needed)								
Cycle 1	X	X	X	X	X	X		See Section 6.2.1.1.1 for details.
Dexamethasone IV or PO								

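### For subjects with an infusion-related reaction above grade 1 on cycle 1 days 1 and 2, the protocol's dilution instructions for the next 16 mg/kg daratumumab infusions conflict, and the concentrations differ twofold

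*Protocol*

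**What the plan says.** Five places in the protocol bear on the volume of the 16 mg/kg infusions.

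- **Synopsis, daratumumab dosage.** For days 1 and 2 of cycle 1, "daratumumab will be administered at 8 mg/kg in 500 mL normal saline each day". For the remaining doses of cycles 1 and 2, "The dose of 16 mg/kg in 500 mL normal saline will be given once weekly as a single infusion". No tolerability condition is attached.
- **Section 6.2.2.1.** The single 500 mL infusion of 16 mg/kg is conditional: "If the subject's first 2 infusions of 8 mg/kg daratumumab are well-tolerated (defined as an absence of infusion-related reaction [IRR] > grade 1". For other subjects, "If the 8 mg/kg infusions are not well-tolerated (defined as IRR > grade 1), the dilution will be in 1000 mL of normal saline", and this lasts until one infusion is completed without an IRR above grade 1. Division of a large-volume dose over two days is permitted, not required. The section sends the reader to Table 13 for the arm 1 schedule.
- **Table 5.** The day 8 column ends at 500 mL and carries footnote a. For subjects who did not tolerate the 8 mg/kg infusions, the footnote says that "the dose may be split in 2 days (on 500 mL each day". It does not state the 1000 mL dilution as a requirement.
- **Table 13 note.** "Thereafter, daratumumab will be given 16 mg/kg per dose diluted in 500 mL NS". Its only section reference for daratumumab concerns medication: "For pre/post-infusion medication guidance, see Sections 6.2.2.1.1 and 6.2.2.1.2".
- **Section 2.5.3.** The initial infusion, and later ones that would otherwise need a large volume such as 1 litre, are to be divided over two days. The verb is *will*, against *may* in Section 6.2.2.1 and footnote a.

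**The concern.** A pharmacy preparing cycle 1 day 8 for a subject who reacted above grade 1 on day 1 or 2 gets a different answer depending on the page it opens. Section 6.2.2.1 leads to 1000 mL. The synopsis and Table 13 lead to 500 mL. Table 5 leads to 500 mL unless the optional split is used. The subjects concerned are those who have just had a reaction.

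For the analysis, the risk is that site practice varies without being visible. The daratumumab data that Section 6.2.2.1 requires on the eCRF are planned and actual dose, start and stop times, reasons for changes, delays and interruptions, and lot number. Diluent volume is not in that list. Repeat IRRs and daratumumab discontinuations among early reactors could therefore not be related directly to the volume they received.

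**Working it through.** **Inputs.** Doses and volumes come from the synopsis, Section 6.2.2.1, Table 5 with footnote a, and Table 13. Rates in mL/hour come from Table 5.

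**1. Reproduce the plan's own figure.** The Table 5 volume for day 8 is the sum of the hourly rates over four hours: 50 + 100 + 150 + 200 = 500 mL. This matches the printed 500 mL. Table 5 has no 1000 mL column.

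**2. Concentration = dose / volume.**

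| Infusion | Where it arises | mg/kg per mL |
|---|---|---|
| 8 mg/kg in 500 mL | Cycle 1 days 1 and 2 | 8/500 = 0.016 |
| 16 mg/kg in 500 mL, one infusion | Synopsis; Table 13; Table 5 without the split | 16/500 = 0.032 |
| 16 mg/kg in 1000 mL | Section 6.2.2.1 after an IRR above grade 1 | 16/1000 = 0.016 |
| 16 mg/kg as 8 mg/kg in 500 mL on each of 2 days (equal halves assumed) | Table 5 footnote a, if the split is used | 8/500 = 0.016 |

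The ratio is 0.032/0.016 = 2.0 at any body weight. The 0.016 figure is also the concentration of the infusions to which the subject reacted.

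**3. Drug delivered per hour = concentration × mL/hour.** Table 5 sets rates by volume, so the twofold ratio carries over at any common rate:

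- at 50 mL/h: 0.032 × 50 = 1.6 against 0.016 × 50 = 0.8 mg/kg/h;
- at 200 mL/h: 0.032 × 200 = 6.4 against 0.016 × 200 = 3.2 mg/kg/h.

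These rates are assumptions for the subjects in question. Footnote a gives the 50 mL/h start for the first 16 mg/kg infusion only where the earlier infusions were tolerated, and no rate is given for the others.

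**4. Total dose.** It is 16 mg/kg in every version. The SAP computes daratumumab dose intensity in mg/kg per week (Section 5, Relative Dose Intensity), so the planned exposure summary does not depend on diluent volume.

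**5. Side by side for a subject with an IRR above grade 1 on day 1 or 2.**

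| Place | Volume | Division over 2 days |
|---|---|---|
| Synopsis | 500 mL | Single infusion |
| Table 13 note | 500 mL | Not mentioned |
| Table 5 and footnote a | 500 mL, or 500 mL on each of 2 days | Optional |
| Section 6.2.2.1 | 1000 mL | Optional |
| Section 2.5.3 | No fixed volume; refers to large volumes, e.g. 1 litre | Stated as what will be done |

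**The case against.** The best defence is that the synopsis and Table 13 give the routine schedule and Section 6.2.2.1 gives the exception. Neither summary mentions subjects who reacted, and the full dosing section is explicit. Footnote a is also attached to the Table 5 entry, and its split yields the same 1000 mL total and the same concentration as Section 6.2.2.1. On this view only a cross-reference is missing.

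Much of that stands: a site that reads Section 6.2.2.1 has a clear dilution rule, and the twofold difference arises only where a site works from another place. It is not a full answer. Section 6.2.2.1 itself directs readers to Table 13, whose note points back only to the medication subsections. An optional split is also not the same instruction as a stated 1000 mL dilution, because a site that declines the split is left with the printed 500 mL.

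A reader might draw four stronger conclusions, which the documents do not support.

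- **That any IRR above grade 1 triggers the conflict.** The 1000 mL rule is tied to the 8 mg/kg infusions and ends after one infusion without such a reaction.
- **That many subjects are affected.** Section 2.4.1 reports reactions to the first infusion in about 50% of patients, but from pooled earlier monotherapy studies and without a grade. The share above grade 1 is given nowhere.
- **That exposure differs, or that reaction rates are shown to depend on volume.** Total mg/kg is the same, and the documents contain no data linking diluent volume to IRRs or discontinuation.
- **That a specific hourly dose is doubled.** This needs a rate that the protocol does not give for these subjects.

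**Conclusion.** The inconsistency is real and limited. It concerns the 16 mg/kg infusions that follow an IRR above grade 1 on cycle 1 day 1 or 2, until one infusion is completed without such a reaction. For those infusions the instructions differ in volume (500 against 1000 mL), in concentration by a factor of 2.0 when the 500 mL dose is not split, and in whether division over two days is optional. The factor rests only on the printed doses and volumes; extending it to hourly delivery assumes equal mL/hour rates.

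The number of subjects affected cannot be estimated from the documents. The practical effect now is probably small: the Amendment 6 rationale says the primary endpoint has been met, so by inference little or no cycle 1 dosing remains. The main value of the correction is a consistent record and safety data that can be interpreted. No judgement is made on which volume or division rule is right.

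**What to change.** Reconcile the synopsis, Section 2.5.3, Section 6.2.2.1, Table 5 with footnote a, and the Table 13 note, so that a subject with an IRR above grade 1 on the 8 mg/kg infusions is covered by one consistent instruction on volume and on division over two days. A pointer to Section 6.2.2.1 in the synopsis and the Table 13 note would be enough there, provided that *may* and *will* are aligned across Sections 2.5.3 and 6.2.2.1 and footnote a. The sponsor decides which instruction is intended.

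The cost is a wording change, plus a short clarification to sites and pharmacies if any such infusions are still to be given. No new data or procedure is needed.
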